ActivPALphysical activity monitors (PALtechnologies, Glasgow, UK) will be used to obtain an objective measure of physical activity (PA). ActivPAL activity monitors assess PA using accelerometry, which allows objective evaluation of the relative volume (steps/day) and intensity (activity counts) of physical activity with high validity and reliability.⁵⁸ Each participant will wear the ActivePAL for 5 consecutive days at all time points to assess average daily PA (steps/day). The ActivPAL monitor will be used only for outcome data (not intervention) and provides no feedback to participants.

| Table 1: Testing measures at each time point | | | | | | | |
|---|----------|------------|-------------|------------|-------------|-------------|-------------|
| | | | Time Points | | | | |
| Outcome Measures | Baseline | 30 days | 60 days | 90 days | 120 days | 150 days | 180 days |
| Primary Outcome: Self-selected gait | Х | Х | Х | Х | | | Х |
| Other Mobility Tests: mPPT, SPPB, | Х | Х | Х | Х | | | Х |
| Activities of Daily Living Performance: | Х | Х | Х | Х | | | Х |
| Home and Community Activity Measures: Life-Space Assessment, ActiGraph Physical Activity Monitors | x | x | x | x | | | x |
| Caregiver Burden: Caregiver Burden | Х | | Х | | | | Х |
| Quality of Life: VR-12 | Х | | Х | | | | Х |

Table 1. Describing the planned study time points and assessments

| AE Reporting Script | х | х | Х | х | Phone | Phone | х |
|------------------------------|---|---|---|---|-------|-------|---|
| Cognition: SLUMS | Х | | Х | | | | Х |
| Patient Motivation: PAM Tool | Х | Х | | | | | |

Nottingham Extended ADL Index (NEADL) will be assessed at each study time-point to assess Instrumental ADL performance of the participants. This measure was chosen because it specifically examines mobility inside and outside the home, domestic tasks, and leisure activities—all of which are highly important tasks when evaluating community dwelling older adults.⁵⁹ The NEADL also has strong psychometric properties. The NEADL has predictive validity for health outcomes after hospitalization in many chronically ill older adult populations.⁶⁰ The test has good construct validity, and also has good test-retest reliability.⁵⁹

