Primary Analysis (Aim 1): The primary analysis will be an intent-to-treat comparison of the differences between treatment groups in change in gait speed 60 days following hospital discharge. Statistical inference regarding the difference between treatment groups will be based on the estimated coefficient for a treatment group indicator variable in a linear regression model with 60 day change in walking speed as the response variable, and explanatory variables that include an indicator of treatment group and the baseline value of gait speed. The baseline gait speed value is included to improve the precision/power of the inference about treatment differences. The conclusion about the statistical significance of differences between groups will be determined by this single statistical test to protect against an elevated risk of false-positive conclusions. Sensitivity analysis will be done to evaluate whether conclusions would differ when other important covariates are added to the model (length of hospital stay, inflammatory molecules, presence of the frailty phenotype [Fried's criteria⁸⁴], days of intensive care unit stay, days of inpatient rehabilitation, age, comorbidity burden, social status, gender]. These variables will be extracted from the VA EMR and stored in the VA version of RedCAP using unique ID numbers for each Veteran. Secondary Analyses (Aim 2): Differences between groups at 60 days following hospital discharge in other outcomes (SPPB, mPPT, PA, dynamometry, LSA, PAM NEADL, CBI, SLUMS, and VR-12) will be analyzed as described above. Follow-up measures at 90 and 180 days will be analyzed to evaluate the long-term impact and sustainability of our PHIT interventions. Secondary analyses will be evaluated for their consistency with the conclusions of the primary endpoints. We anticipate that group differences in secondary measures will be correlated with the primary so that significant differences in the primary endpoint will be reinforced by similar effects on secondary endpoints. Failure to observe consistency in the primary and secondary endpoints will be taken as evidence that the effects of PHIT are not clear, and that further study is necessary to resolve any inconsistencies. This approach will reduce the risk of false-positive conclusions resulting from multiple statistical tests.

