The characteristics of the time trajectory (30, 60, 90 and 180 days of follow-up) for treatment effects will also be analyzed in secondary analyses to elucidate the mechanism and inform the

development of methods to improve long-term outcomes. The analytic methods will include maximum likelihood estimates from a repeated measures model of the mean effect at each of the measurement times.⁸⁵ The trend in means will be evaluated using a linear contrast as the summary measure of greatest interest.⁸⁶ This approach will evaluate whether there are differences in the first-order trends (slope) between intervention groups. Finally, we will estimate adverse events rates (falls, emergency department visits, nursing home days, or rehospitalizations) for each arm and compare rates between arms using a likelihood ratio test. We will additionally investigate whether training volume significantly explained additional variability in functional gains within the PHIT group using regression analysis.

Sample Size Estimates

Statistical power was estimated based on the results of a pilot study of 18 participants: 8 were randomized to PHIT, 10 to the UC interventions (results for SPPB, gait speed, and mPPT are shown in Figure 2). We observed a between group difference \pm SD in gait speed of 0.18 \pm 0.29 meters/second (m/s) in the preliminary study. Thus, a sample size of 112 patients completing the study (56/group) will provide 90% power (assuming the same pooled SD in both groups to be conservative) to detect differences at least that great. This represents 1.8 times a clinically important difference of 0.1m/s.⁴⁶ This estimate is conditional upon using a 2-sided, alpha = 0.05 level 2-group t-test.

We expect that we will consent 250 Veterans and spouses for the study, with allowance for a 25% screening failure. Screening failures that occur after consent is obtained and before enrollment in the study may include a change in medical status during hospitalization requiring a discharge to a location other than home health (e.g skilled nursing facility), a hospital re-admission which occurs after hospital discharge but prior to the baseline assessment being completed, or a failure to meet specific performance inclusion criteria (e.g. a Veteran or spouse who lacks the ability to ambulate 10 feet without at least minimal physical assistance [more than supervision or light touching for steadiness] from another person)

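### Could a flat treatment-difference slope over days 30 to 180 make a sustained 60-day benefit count as inconsistent?

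*Combined protocol and SAP*

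**What the plan says.** All the relevant text is in section F (Data Analysis Plan) of the combined protocol and SAP.

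- **Primary test.** One regression of the 60-day change in gait speed on treatment group and baseline gait speed. Statistical significance rests on that test alone.
- **Consistency rule.** "Secondary analyses will be evaluated for their consistency with the conclusions of the primary endpoints". The plan expects that "significant differences in the primary endpoint will be reinforced by similar effects on secondary endpoints", and adds: "Failure to observe consistency in the primary and secondary endpoints will be taken as evidence that the effects of PHIT are not clear". Consistency is not defined.
- **Later visits.** Days 90 and 180 are analysed in their own right for long-term impact and sustainability.
- **Time course.** "The characteristics of the time trajectory (30, 60, 90 and 180 days of follow-up) for treatment effects" are a secondary analysis whose stated aims are mechanism and better long-term methods. The method is "maximum likelihood estimates from a repeated measures model of the mean effect at each of the measurement times", followed by "The trend in means will be evaluated using a linear contrast as the summary measure of greatest interest", which tests whether slopes differ between the arms.

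No contrast scores are given. Baseline is not among the listed follow-up days, but it is a column of Table 1 ("Outcome Measures | Baseline | 30 days | 60 days | 90 days").

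**The concern.** The sentence that opens the consistency rule covers secondary analyses without exception, and the time course is described as one: "for treatment effects will also be analyzed in secondary analyses to elucidate the mechanism". A contrast over four follow-up visits is blind to a difference that is the same at every visit. If PHIT works by day 30 and the gain is fully kept, the expected slope difference is zero. A null slope is then what success looks like, while the rule looks for similar effects. Read literally, a significant and lasting 60-day gain could be reported as unclear because the leading trend summary was null.

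The unstated form adds to this. The visits are unequally spaced, and if baseline entered as a fifth response, the slope would turn from a measure of fading into something closer to a measure of overall benefit. For some patterns its sign would change.

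**Working it through.** **Inputs from the Sample Size Estimates:** difference 0.18 m/s, SD 0.29 m/s, 56 completers per arm, two-sided 5%. **Assumed, because the documents do not give them:** the same SD and 56 per arm at every visit, equal between-visit correlation ρ of 0.5, 0.8 or 0.9, and every effect other than 0.18 at day 60. Dropout between visits is ignored.

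**1. The plan's own figure.** SE = 0.29 × √(2/56) = 0.0548. Then 0.18/0.0548 = 3.28, and power = Φ(3.28 − 1.96) = 0.907 (0.902 by noncentral t). The stated 90% reproduces. Under the same SD and n, a kept 0.18 m/s gives the day-180 comparison the same 91%.

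**2. Slope over the listed days, scored by actual time.** The mean day is 90, so the centred scores c are −60, −30, 0, 90, with Σc² = 12,600. With dⱼ the group difference at visit j:

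- slope × 150 days = 150 × Σcⱼdⱼ / 12,600
- SE = 150 × 0.29 × √[(2/56)(1 − ρ)/12,600] = 0.0518 / 0.0328 / 0.0232 for ρ = 0.5 / 0.8 / 0.9
- correlation of the 60-day difference with the slope = (−30/√12,600) × √(1 − ρ) = −0.19 / −0.12 / −0.08

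The last column below uses the bivariate normal distribution. For example, with constant 0.18 and ρ = 0.5, the joint probability of a significant 60-day test and a non-significant slope is 0.863, and 0.863/0.907 = 95%.

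| Difference at days 30, 60, 90, 180 | Slope × 150 days (m/s) | Slope non-significant, given a significant 60-day test (ρ = 0.5 / 0.8 / 0.9) |
|---|---|---|
| 0.18, 0.18, 0.18, 0.18 | 0 | 95% / 95% / 95% |
| 0.15, 0.18, 0.18, 0.18 | +0.021 | 94% / 90% / 85% |
| 0.10, 0.18, 0.18, 0.18 | +0.057 | 81% / 59% / 31% |
| 0.05, 0.18, 0.18, 0.18 | +0.093 | 58% / 20% / 2% |

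Third row: −60(0.10) − 30(0.18) + 90(0.18) = 4.8, and 150 × 4.8/12,600 = 0.057.

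With 0.18 kept from day 60, the sum reduces to 60 × (0.18 − d₃₀). It is zero only if the day-30 difference is already 0.18. Hypothesis 1.1 predicts a further rise from day 30 to day 60. In the pilot (section D1.4), usual care worsened over that interval while PHIT kept improving. The first row is therefore not the pattern the plan expects.

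**3. What the slope detects and misses.** If the benefit is gone by day 180 (0.18, 0.18, 0.18, 0), slope × 150 = −0.193, significant in 96% to over 99% of trials. A rise followed by partial fading can still give zero: for 0.09, 0.18, 0.18, 0.12 the sum is −5.4 − 5.4 + 0 + 10.8 = 0. A null slope alone does not prove persistence; the visit-specific differences are needed to read it.

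**4. Baseline.** Contrast scores sum to zero. Subtracting a patient's baseline from every follow-up value, or adjusting for it with one common coefficient, therefore cancels from the slope. Only baseline as a fifth response changes the result. The scores become −72, −42, −12, 18, 108 (Σc² = 19,080). A constant 0.18 then gives slope × 180 = 180 × 12.96/19,080 = +0.122, significant in 68% / 97% / over 99%. Loss of benefit by day 180 gives −0.061, detected in only 23% / 48% / 77%. For 0.12, 0.18, 0.15, 0.09 the slope is −0.054 over 150 days without baseline and +0.049 over 180 days with it.

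**5. The text of the rule.** The expectation and the consequence are both worded for endpoints. The secondary outcomes listed at the start of section F are measures such as SPPB, mPPT and LSA; a slope contrast on gait speed is not one of them. Nothing defines inconsistency as a non-significant p-value.

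**The case for a change.** The best case for a change is that the scope sentence names analyses and exempts none, that the rule shapes the trial's conclusion, and that two sentences written before unblinding would settle both the slope's role and its form at no cost. Steps 3 and 4 also show that, for some effect patterns, two analysts could report different things about fading from the same data.

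Part of this stands. The scores, the place of baseline and the reading of the slope are not written down, and the choice can matter. The step from there to a wrong conclusion does not stand. It needs the endpoint rule to reach a mechanistic contrast, and it needs a null slope to count as disagreement; the plan states neither. The fifth-response reading is strained, because the plan names four follow-up days for treatment effects and a pre-treatment visit has no treatment effect to trend. The natural default is a contrast in actual days over those four visits, with baseline as a covariate as in the primary model.

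**Conclusion.** No change follows; this is missing detail that a competent analyst supplies. Beside a positive 60-day result, a null slope is read together with the planned day-90 and day-180 comparisons and the visit-specific effects from the same model. If those hold up, it means persistence, which agrees with Hypothesis 1.1.

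The 95% figure requires the day-30 effect to equal the day-60 effect. Under the predicted rise the rate runs from 94% down to 2%, depending on a day-30 effect and a correlation that the documents do not give, so no firm size can be attached. The single primary test and its power of about 90% are untouched, as are the later comparisons that carry the persistence claim (about 91% power at day 180 if 0.18 m/s is kept with the same SD and 56 per arm). Writing down the scores and the role of baseline would be tidy, but sound conclusions do not depend on it.

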Title: Improving Function in Older Veterans With Hospital-Associated Deconditioning

NCT: 02696382

Version Date: 05.23.2022

Protocol #: 15-1571 Project Title: Improving function in older Veterans with hospital-associated deconditioning Principal Investigator: [name], PT, PhD Version Date: 05.23.2022

I. Hypotheses and Specific Aims:

Hospitalization with subsequent deconditioning (hospital-associated deconditioning) is a common and profound contributor to functional decline in older adults.¹⁻³ Skeletal muscle weakness and atrophy are commonly observed in older adults with deconditioning after a hospitalization,^{2,4,5} leading to development of chronic functional deficits. This is especially concerning for elderly Veterans, a population who has lower physical function⁶ and more comorbidities^{7,8} at baseline than the general older adult population, and therefore may be at even higher risk for developing disability in activities of daily living (ADLs) after hospitalization.⁹ Thus, our research has the following aims

Specific Aim 1: To determine if PHIT training, initiated upon discharge from an acute care hospital, is as safe and more effective than UC in promoting sustained gains in physical function for older Veterans.

Hypothesis 1.1: There will be greater improvements in gait speed (primary outcome), Short Physical Performance Battery Scores (SPPB), modified Physical Performance Test (mPPT), Timed Up and Go test (TUG), grip strength, and knee extensor muscle strength in the PHIT group compared to the UC group at 60 days following hospital discharge, without increasing adverse events. Benefits of PHIT will be apparent at the end of intervention (30 days), will increase further at 60 days (primary endpoint), and will persist at 90 and 180 days.

Specific Aim 2: To determine if PHIT intervention, initiated upon discharge from an acute care hospital, improves independence in home and community mobility more than UC in older Veterans.

Hypothesis 2.1: There will be greater recovery in the PHIT group in measures of home and community mobility, as measured by the Nottingham Extended ADL Index, physical activity (PA) monitors, and the Life-Space Assessment (home and community mobility). Assessments will be performed at all time-points.

Specific Aim 3: To determine if PHIT rehabilitation, initiated upon hospital discharge, improves Veteran quality of life (QOL) & cognition, with concomitant reduction in caregiver burden compared to UC.

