The Life-Space Assessment (LSA) is a self-report measure assessing a patient's movements, extending from within the home to movement beyond a patient's town or geographic region.⁶¹ The life-space assessment is a continuous measure which can be scored from 0 (totally bedbound and dependent with all activity) to 120 (independent with community ambulation without assistance). The scores take into account both the performance of movement within and outside the home, the frequency of the movement, and the amount of assistance required. Specifically, this measure allows evaluation of actual mobility performed in the home and community, and can be evaluated for older adults across all levels of function. LSA has concurrent validity with physical function measures, as well as self-reported health and ADL disability.⁶² The Life-Space Assessment has good test-rest-reliability (ICC=0.96), and is responsive to change in community-dwelling older adults.⁶¹

Quality of Life and Caregiver Burden (Aim 3)

The Veterans RAND 12 Item Health Survey (VR-12) will be used to assess the quality of life in Veterans. The SF-12 has strong concurrent validity with well-established quality of life measures and is reliable for assessing changes in quality of life in community dwelling adults.⁶³

The Caregiver Burden Inventory (CBI) is a multi-dimensional 24-item scale with a five-point scoring system from 0 (never) to 4 (nearly always). The subscales of the CBI demonstrate strong convergent validity with caregiver depression, caregiver satisfaction, and number of caregiver tasks.³¹

Adverse Events Reporting Script will be used to assess any adverse events (e.g. ER visit(s), hospitalization(s), major illness/injury) which occurred since the last study visit and whether the participant is completing their exercises. The AE script will be administered 7 times, once at each of the 5 study visits, and once during each of 2 phone calls.

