All assessments and interventions in this study are considered to be a part of physical therapist clinical practice. We see little or no additional risk resulting from participation in this study. To minimize risk of falls and injury, the PHIT training protocol will be conducted with licensed physical therapists (PTs) trained to minimize risk of falls and will not be undertaken in subjects who report inability to perform the tasks. In all conditions of outcome testing in which the participant is standing and/or walking (e.g. conditions with a potential risk for falling), the participant will be directly supervised by a member of the research staff (PRA or research physical therapist) who has been trained on all measures by a physical therapist, and a licensed physical therapist will be available by telecommunication at all times.

There is no expectation that the proposed multi-component intervention will evoke serious cardiovascular responses. Gardner et al⁸⁰ reviewed controlled clinical trials with exercise interventions for older adults at-risk for falling. No cardiac events or falls were reported in the 12 clinical trials reviewed. No significant cardiac events were reported after performing one repetition maximum (1-RM) testing for over 6600 healthy subjects.⁸¹ A recent review of 12 articles examining the safety of high intensity resistance training and testing in persons with coronary disease found an absence of anginal symptoms, ischemic ST-segment depression, abnormal hemodynamics, complex ventricular dysrhythmias, and cardiovascular complications.⁸² Less serious risks may include chest pain, fainting, hypotension, or muscle strain.

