We have minimized risk to patients who are not undergoing exercise stress tests by following the guidelines suggested by Gill et al. which are outlined below.⁸³ Every effort will be made to prevent adverse events including stopping exercise when the patient reports shortness of breath, angina or dizziness. A licensed physical therapist will supervise all of the training sessions and will additionally monitor blood pressure at the start of the training session, mid-session, and when participants are finished with the session. Blood pressure and heart rate will be monitored using a standard blood pressure cuff and palpation of peripheral pulse. If blood pressure is elevated above 160/100, the participant will rest quietly for a few minutes. The PT will monitor the patient for signs of muscle strain, dizziness, or hypotension. As needed, appropriate palliative methods will be discussed with the participants and reported to the primary care physician, although these adverse events are also not expected. All PTs and PRAs will be trained in a standardized way to address all safety precautions.

Delayed onset muscle soreness is a common occurrence after the initiation of an exercise program. The soreness occurs in the muscle belly 1-3 days after the initiation of exercise and lasts 2-3 days. There is no effective way to eliminate the risk of delayed onset muscle soreness, but it is hoped that the orientation process and gradual increase in intensity will reduce the risk. The participants will be informed about the condition, what it feels like, how long it lasts, and suggested ways of decreasing the pain including the use of superficial heat or ice.

There is also a small risk of rash on the area of skin on which the TegaDerm patch is applied. We anticipate that these risks are minimal, and have low potential for any long-term harm. Nonetheless, if any abnormal skin reactions are observed, we will notify either the home health agency nursing staff, the patient's physician, or a study physician to determine the appropriate medical care.

Other outcome assessments are also expected to be minimal risk to participants. Use of ActiGraph monitors to assess physical activity is common in older adult populations, and has not been associated with adverse events of a serious nature. Physical therapists treating patients will monitor for skin irritation over the areas where the Actigraph straps come into contact with skin and discontinue use if any skin breakdown occurs.

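### The between-arm safety comparison omits the exercise harms named in the risk section other than falls, and no supplied text carries in-session events into it

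*Combined protocol and SAP*

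**What the plan says.** - **Objective.** Section I, Specific Aim 1, asks whether PHIT "is as safe and more effective than UC in promoting sustained gains in physical function for older Veterans". Hypothesis 1.1 expects the functional gains "without increasing adverse events". No margin or decision criterion for safety is given.
- **Analysis.** The Data Analysis Plan (IV.F) has one between-arm safety comparison: "we will estimate adverse events rates (falls, emergency department visits, nursing home days, or rehospitalizations) for each arm and compare rates between arms", by a likelihood ratio test.
- **Named harms.** Section IV.C speaks of falls and injury ("To minimize risk of falls and injury, the PHIT training protocol will be conducted with licensed physical therapists") and then says "Less serious risks may include chest pain, fainting, hypotension, or muscle strain". It adds dizziness among the signs the treating therapist watches for, and says "Delayed onset muscle soreness is a common occurrence after the initiation of an exercise program".
- **In-session route.** For strain, dizziness and hypotension, IV.C says: "As needed, appropriate palliative methods will be discussed with the participants and reported to the primary care physician". The same sentence classes them as adverse events, though unexpected ones.
- **Study-level capture.** The Adverse Events Reporting Script (IV.A) "will be used to assess any adverse events (e.g. ER visit(s), hospitalization(s), major illness/injury) which occurred since the last study visit". It is given at five visits and two telephone calls.
- **Session records.** Section D2.6 has therapists faxing documentation weekly and research therapists reviewing the intervention data sheets every two weeks. Both are described as checks on treatment fidelity.

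**The concern.** The two arms are matched on visits and time and are meant to differ in exercise intensity (D2.5). Table 2 sets sets-to-failure at 74-104 lbs against no resistance, 0-2 lb weights or low-resistance bands. The harms most directly tied to that contrast are strains, faints, chest pain, drops in blood pressure and sessions cut short for symptoms. If the analysis follows the stated list, PHIT could produce more of these than usual care and the trial could still report no increase in adverse events.

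That would leave a question the sponsor itself raises unanswered. Section II (B.5) reports that therapists avoid intensive training partly because they fear injuring patients. Elsewhere Section II says the trial should counter the belief that conservative treatment is safer at home. Section III (D1.4) credits the pilot with showing no added injury risk. Injury is not a compared category, so the planned comparison cannot confirm that claim.

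**Working it through.** **1. Named harms against the compared list**

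| Harm | Named in IV.C | Compared in IV.F | Among the script's examples (IV.A) |
|---|---|---|---|
| Falls | yes | yes | no |
| Injury | yes | no | only if major |
| Chest pain | yes | no | no |
| Fainting | yes | no | no |
| Dizziness | yes | no | no |
| Hypotension | yes | no | no |
| Muscle strain | yes | no | only if a major injury |
| Delayed soreness | yes | no | no |
| Death | no | no | no |

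A harm marked no in the third column enters the comparison only through an emergency department visit, nursing home days, a rehospitalization or a fall. This gap does not depend on capture: a perfectly recorded strain would still not be compared.

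**2. Capture**

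The intervention lasts 4 weeks (D2.5). Table 1 places the script at baseline and next at 30 days, so one retrospective report by the participant covers most of the 10-12 sessions. The person who sees an in-session event is the treating therapist. The stated report from the therapist goes, as needed, to the primary care physician. Session paperwork reaches the research therapists, but no supplied sentence moves an event from it to the adverse event record. The list of expected events that closes IV.C names falls and complications of existing conditions, but none of the symptoms above.

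**3. The plan's own figure**

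The only power statement is for gait speed, and it reproduces. With difference 0.18 and SD 0.29 m/s, n per group = 2 x (1.960 + 1.282)^2 x 0.29^2 / 0.18^2 = 54.6, rounded up to 55. The t-test version gives 55.5, so 56. Power at 56 per group is 90.2% (t-test). 112 / 0.75 = 149.3, which supports 150 enrolled. Nothing comparable is given for safety, and the fix changes none of these numbers.

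**4. Scale, by illustration only**

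150 / 2 = 75 enrolled per arm. Planned sessions are 75 x 10 = 750 to 75 x 12 = 900 per arm, an upper figure because it assumes full attendance. The documents give no rates for these harms. Assume 10% of PHIT and 2% of usual-care participants have a strain or faint without a listed consequence: 75 x 0.10 = 7.5 and 75 x 0.02 = 1.5 people. None is compared, which follows from how the example is defined.

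**5. What adding them could show**

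Power for two proportions, two-sided 0.05, all rates assumed: z = [|p1 - p2| - 1.96 x sqrt(2 x pbar x (1 - pbar) / n)] / sqrt([p1(1 - p1) + p2(1 - p2)] / n), where pbar is the mean of p1 and p2, and power is the normal probability below z.

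| Assumed rates | 75 per arm | 56 per arm |
|---|---|---|
| 5% v 10% | 21% | 17% |
| 5% v 15% | 53% | 42% |
| 5% v 20% | 80% | 67% |
| 10% v 20% | 40% | 32% |
| 10% v 30% | 87% | 76% |

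If both arms truly had 5%, the 95% half-width for the difference would be 1.96 x sqrt(2 x 0.05 x 0.95 / 75) = 0.070, or 7.0 percentage points (a rough normal approximation at these counts). Equal observed rates would still be compatible with a PHIT excess of about 7 points.

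**The case against.** **Is the reporting route really closed?** A reader might infer that in-session harms go to the primary care physician and nowhere else. The documents do not say that. IV.C names that physician without excluding others. Therapists fax records weekly, research therapists review data sheets and hold monthly calls, and the withdrawal criteria assume that new conditions become known to a physician, safety officer or investigator. What stands is narrower: none of these channels is described as feeding adverse event data.

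**Does the script exclude minor harms?** No. It asks about any adverse event, and its examples are only examples. A strain or faint could be recorded. But the examples point to serious events, and recording does not bring a harm into the IV.F list.

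**Do the supervised sessions add nothing to the safety comparison?** A reader might infer this, but it goes too far. A fall in a session, or any session event that leads to an emergency visit or rehospitalization, would count. Falls are an exercise risk named in IV.C, and they are compared.

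**The forms are not visible.** IV.A says copies of each tool are attached, and D2.5 and D2.6 refer to an Appendix for intervention and fidelity detail. The supplied text includes neither. The visit sheet may already hold symptom fields and the script may ask about falls. This limits any firm statement about capture, but leaves the gap in the analysis list.

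**Would the addition be worth much?** Treating therapists know the arm and may report minor events differently, and power is low for modest differences. Both points stand. They argue for reporting estimates with intervals and having a second source, not for leaving the harms out.

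**Conclusion.** The point holds as a gap between the safety objective and the safety analysis. Of the exercise harms named in IV.C, only falls are compared between arms. Chest pain, fainting, dizziness, hypotension and muscle strain or injury count only through a listed consequence, and death is not listed. This rests on reading the parenthesis in IV.F as the list of compared events, which is its plain sense.

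The capture point is weaker. No supplied text routes in-session events into the adverse event record or the analysis, but the script could collect them and the forms cannot be checked.

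The size of any missed difference is unknown because the documents give no rates; the 10% against 2% example only shows scale. Adding the harms would let the trial estimate them. On the assumed rates above, it would not by itself establish equal safety, for which no criterion is stated.

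**What to change.** - **IV.F.** Add, per arm, the number of participants with any exercise-related event (chest pain, fainting or dizziness, hypotension, muscle strain or injury, a session stopped for symptoms) and the number of deaths, each with the between-arm difference and a confidence interval. Present these as estimates. Report delayed soreness descriptively.
- **Per-visit sheet.** If they are not already there, add the same items in identical wording for both arms, and send them to the study team as well as the primary care physician.
- **Adverse event script.** Ask both arms about the same symptom items, plus falls, nursing home days and death, so that it can serve as a cross-check on therapist reports.

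The cost is a revision of two forms and a sentence or two in the analysis plan. Therapists already document visits and fax weekly, and no dose, stopping rule or sample size changes. The main downside is differential reporting by unblinded therapists. The script items reduce that problem without removing it, since they rest on participant recall and participants also know what treatment they received.
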